#### **4.3.2. Stopping a Patient's Study Participation**

##### **4.3.2.1. Patient or Legal Guardian Stops Participation in the Study**

A patient or their legal guardian may stop participation in the study at any time. A patient/legal guardian considering stopping participation in the study should be informed that they can discontinue study drug and/or decline procedural assessments and remain in the study to complete their study assessments through the Week 36 visit, including entering the 52-week safety follow-up. If a patient/legal guardian still chooses to discontinue study drug and stop participation in all follow-up prior to the completion of the 36-week treatment period, every effort should be made to conduct early the assessments scheduled to be performed at the Week 36 EOS/ET visit (see [Table 1](#)).

If the patient does not wish to or is unable to continue further study participation, the investigator is to discuss with the patient appropriate procedures for stopping participation in the study. Data collected from the patient can continue to be used.

In addition, in the countries where the collection and processing of the patient data is based on the patient consent, if a patient withdraws consent to collect and process his/her data (see Section [4.3.2.2](#)), as applicable, patient data up to the withdrawal of consent will be included in the analysis of the study. In addition, where permitted, publicly available data (such as appropriate national or regional vital status registry or other relevant databases) can be included after withdrawal of consent, where available and allowable by local law.

#### **4.3.2.2. Withdrawal of Consent to Process the Patient's Personal Data**

Where allowed by local law, the patient may decide to withdraw consent to collect, store and use biological samples and, as applicable, other personal data, informing the study doctor at any time in writing or in any other form that may be locally required. The Sponsor will continue to keep and use the patient's study information (including any data resulting from the analysis of patient's biological samples until the time of withdrawal) according to applicable law. The process for the storage and, as applicable, further use of remaining samples will be followed per local requirements.

#### **4.3.2.3. Investigator or Sponsor Stops Participation of a Patient in the Study**

The Investigator or Sponsor may stop the participation of a patient in the study at any time if this is considered to be in the patient's best interest. However, study integrity and interpretation are best maintained if all enrolled patients continue study assessments and follow-up even if study drug is discontinued.

Termination of the clinical study and site closure are described in Section [8.1.6](#).

#### **4.3.2.4. Recording Reason for Stopping a Patient's Study Participation**

The primary reason that a patient's study participation is stopped must be recorded in the appropriate section of the eCRF and all efforts will be made to complete and report the observations as thoroughly as possible. If a patient's study participation is stopped due to an adverse event (AE), including serious adverse events (SAEs), the event should be followed as described in Section [6.7.6](#).

### **4.3.3. Lost to Follow-Up**

A patient will be considered lost to follow-up if the patient repeatedly fails to return for scheduled visits and is unable to be contacted by the clinical study center. The following actions must be taken if a patient fails to return to the clinic for a required study visit:

- The site must attempt to contact the patient or legal guardian and reschedule the missed visit as soon as possible and counsel the patient or legal guardian on the importance of maintaining the assigned visit schedule and ascertain if the patient or legal guardian wishes to continue in the study, and/or should continue in the study.
- Before a patient is deemed lost to follow up, the investigator or designee must make every effort to regain contact with the patient or legal guardian (where possible, 3 telephone calls and, if necessary, a certified letter to the patient's last known mailing address or local equivalent methods). These contact attempts should be documented in the patient's medical record.
- Should the patient or legal guardian continue to be unreachable, the patient will be considered to have stopped participation in the study.
- For patients who are lost to follow-up, the Investigator can search publicly available records (where permitted and allowed by local law) to ascertain survival status. This ensures that the outcome of the study is as comprehensive as possible.

#### 4.3.4. Replacement of Study Patients

Patients who discontinue the study drug or stop participation in the study during the 36-week treatment period or the OLE will not be replaced.

## 5. TREATMENTS AND OTHER REQUIREMENTS

### 5.1. Treatments Administered

Study drug supplied for this study must not be used for any purpose other than the present study and must not be administered to any person not enrolled in the study. Study drug that has been dispensed to a patient and returned unused must not be re-dispensed to a different patient.

### 5.2. Study Drug

Detailed information describing the preparation, administration, and storage of cemdisiran and placebo is provided in the Pharmacy Manual.

#### 5.2.1. Description

Cemdisiran will be supplied as a sterile solution for SC injection that contains 200 mg/mL cemdisiran sodium (equivalent to 189 mg/mL of cemdisiran), formulated in water for injection (WFI) for SC administration. See the Pharmacy Manual for further details of solution concentration and fill volume.

The control drug for this study will be a placebo (sodium chloride 0.9% w/v for SC administration). Placebo will be provided by the Sponsor; it will be packaged identically to cemdisiran.

#### 5.2.2. Dose and Administration

Patients will be administered cemdisiran (600 mg) or placebo (at the same volume as the active drug) as an SC injection once every 4 weeks in combination with standard of care in the 32-week treatment phase. During the 52-week OLE phase, patients will be administered cemdisiran at a dose of 600 mg every 4 weeks in combination with standard of care.

Study drug injections will be administered under the supervision of the Investigator or healthcare professional. At-home dosing may be administered by a healthcare professional. The injection site may be marked and mapped for later observation. The preferred site of injection is the abdomen. Optional additional sites are the upper arms and thighs. If a local reaction around the injection site occurs, photographs may be obtained, if permitted. Detailed instructions for study drug administration are found in the Pharmacy Manual.

To maintain the blind during the treatment period, the syringes are to be masked prior to study drug withdrawal. A full description of the blinding procedure is included in the Pharmacy Manual.

#### 5.2.3. Dose Modifications

Dose modifications are not permitted.

If a study drug-related AE occurs in a patient that the Investigator judges as presenting a potential risk to the patient for further dosing, the study drug dose may be held at the discretion of the Investigator and the Medical Monitor should be contacted.

### 5.2.3.1. LFT Criteria for Withholding, Monitoring and Stopping Cemdisiran Dosing

1. LFT results ([Table 5](#)) from the previous visit should be reviewed prior to dosing. Central laboratory results are preferable. If not available, local laboratory results may be used; however, if a local assessment is drawn, a serum chemistry sample must also be drawn for analysis at the central laboratory.
2. For any ALT or AST elevation  $>3 \times \text{ULN}$ , central laboratory results should be used to guide subsequent monitoring as detailed in [Table 4](#).
3. For any ALT or AST elevation  $>3 \times \text{ULN}$ :
  - a. Confirm using central laboratory, as soon as possible, ideally within 2 to 3 days, but no later than 7 days.
  - b. Perform assessments per [Table 4](#) and [Table 6](#).
  - c. If an alternative cause is found, provide appropriate care.
4. For any ALT or AST elevation  $>3 \times \text{ULN}$  without alternative cause that is accompanied by clinical symptoms consistent with liver injury (eg, nausea, right upper quadrant abdominal pain, jaundice) or elevated bilirubin to  $\geq 2 \times \text{ULN}$  or INR  $\geq 1.5$ , permanently discontinue dosing.
5. For confirmed ALT or AST elevations  $>3 \times \text{ULN}$  without alternative cause and not accompanied by symptoms or elevated bilirubin  $\geq 2 \times \text{ULN}$  or INR  $\geq 1.5$ , see [Table 4](#)

**Table 4: Monitoring and Dosing Rules for Asymptomatic Patients with Confirmed Isolated Elevations of ALT and/or AST  $>3\times$  ULN, with No Alternative Cause Identified**

Transaminase Level	Action
$>3\times$ to $5\times$ ULN	

May continue dosing

Evaluate the initial elevation in LFT per the following assessments:

Table 6 (all assessments to be performed once)

Hematology, serum chemistry, LFT, and coagulation per Table 5

Monitor at least every two weeks: LFT and coagulation per Table 5

If elevation persists for <math>\geq 2</math> months, must discuss with the Medical Monitor before continuing dosing

$>5\times$ to $8\times$ ULN	

Hold cemdisiran dosing until recovery to <math>\leq 1.5\times</math>ULN; may resume dosing after discussion with the Medical Monitor

Evaluate the initial elevation in LFT per the following assessments

Table 6 (all assessments to be performed once)

Hematology, serum chemistry, LFT, and coagulation per Table 5

Monitor at least weekly: LFT and coagulation per Table 5 until ALT and/or AST is declining on 2 consecutive draws, then may decrease monitoring to biweekly

If ALT or AST rises to <math>>5\times</math>ULN following resumption of dosing, permanently discontinue dosing

$>8\times$ ULN	Permanently discontinue dosing after confirmation of the transaminase value

Abbreviations: ALT=alanine transaminase; AST=aspartate transaminase; INR=international normalized ratio; LFT=liver function test(s); ULN=upper limit of normal.

Notes: In addition to these criteria, other assessments or evaluations may be performed per Investigator discretion, as appropriate.

#### 5.2.4. Preparation, Handling, and Storage

Staff at each clinical study center or the home healthcare professional will be responsible for preparation of cemdisiran doses, according to procedures detailed in the Pharmacy Manual. No special procedures for the safe handling of study drug are required.

Study drug will be stored upright and refrigerated at approximately 2 to 8°C. The vial should be stored in the carton until ready for use in the storage area of the clinical study site pharmacy, in a secure, temperature-controlled, locked environment with restricted access. Deviations from the recommended storage conditions should be reported to the Sponsor and use of the study drug halted until authorization for its continued use has been provided by the Sponsor or designee, as described in the Pharmacy Manual.

A Sponsor representative or designee will be permitted, upon request, to audit the supplies, storage, dispensing procedures, and records.

Instructions specific to unused study drug and additional storage will be provided in the Pharmacy Manual.

### **5.2.5. Packaging and Labeling**

All packaging, labeling, and production of study drug will be in compliance with current Good Manufacturing Practice specifications, as well as applicable local regulations. Study drug labels and external packaging will include all appropriate information as per local labeling requirements.

Cemdisiran (solution for SC injection) is packaged in 2-mL glass vials with a fill volume of no less than 0.55 mL to allow for complete withdrawal of a 0.5-mL of drug product at the pharmacy. The container closure system consists of a Type I glass vial, a Teflon-faced 13-mm stopper, and a flip-off aluminum seal.

Additional details will be available in the Pharmacy Manual.

### **5.2.6. Accountability**

The Investigator or designee will maintain accurate records of receipt and the condition of the study drug supplied for this study, including dates of receipt. In addition, accurate records will be kept of when and how much study drug is dispensed and administered to each patient in the study. Any reasons for departure from the protocol dispensing regimen must also be recorded.

At the completion of the study, there will be a final reconciliation of all study drugs. Used, partially used, and unused study drug will be returned to the Sponsor (or designee) or destroyed at the clinical study center according to applicable regulations.

Further instructions about drug accountability will be detailed in the Pharmacy Manual.

## **5.3. Concomitant Medications and Procedures**

The standard of care treatment should be held stable throughout the run-in and treatment periods. Use of concomitant medications and procedures will be recorded on the patient's eCRF as specified in the Schedule of Assessments (see [Table 1](#) and [Table 2](#)). This includes all prescription medications, herbal preparations, over the counter medications, vitamins, and minerals. Any changes in medications during the study will also be recorded on the eCRF.

If patients use nonsteroidal anti-inflammatory drugs intermittently or chronically, they must have been able to tolerate them with no previous side effects (eg, gastric distress or bleeding).

Standard vitamins and topical medications are permitted. However, topical steroids must not be applied anywhere near the injection site(s) unless medically indicated.

For other permitted concomitant medications administered SC, do not administer in same injection site area as the study drug/placebo, for 7 days after the last dose of either study drug or placebo.

Any concomitant medication that is required for the patient's welfare may be administered by the Investigator. However, it is the responsibility of the Investigator to ensure that details regarding the medication are recorded on the eCRF. Concomitant medication will be coded using an internationally recognized and accepted coding dictionary.

### **5.3.1. Prohibited Concomitant Medications**

The following concomitant medications are prohibited during the study:

- Systemic steroids (short-term steroid course for <7 days for common conditions not related to IgAN (i.e. asthma, gout) is permitted)
- Immunosuppressive agents
- Fish oil supplements (if started prior to Screening, then may continue during the study at the same dose)
- Hydroxychloroquine

### 5.3.2. Study-specific Vaccinations

#### 5.3.2.1. Meningococcal Vaccinations

All patients taking part in this study must be vaccinated against meningitis types A, C, W135, Y and B, upon determination of eligibility at the end of run-in period, 2 weeks prior to randomization to cemdisiran or placebo, as per the Schedule of Assessments. Meningococcal group ACWY conjugate vaccine and meningococcal group B vaccine will be administered in accordance with the manufacturer's instructions and according to the Advisory Committee on Immunization Practices (ACIP) or other locally applicable recommendations for patients with complement deficiencies. On days of vaccination, urinary samples should be collected prior to administration of vaccines.

Patients will be immunized against *Neisseria meningitidis* according to the following specifications:

- Patients who have previously completed the recommended series of meningococcal vaccinations (meningococcal group ACWY conjugate vaccine and meningococcal group B vaccine) at least 14 days but no more than 3 years from randomization can start study assessments after confirming eligibility. Documented vaccine history must be available to, and verified by, study site staff at the time of Screening.
- Patients who were previously vaccinated with polysaccharide type vaccines within 3 years of study entry will be revaccinated using conjugate vaccines if found eligible at the end of the run-in period.
- Patients who have not been previously vaccinated against *Neisseria meningitidis*, those without documentation of vaccination history, or those vaccinated more than 3 years from study randomization will commence the vaccination series with the recommended meningococcal vaccines (meningococcal group ACWY conjugate vaccine and meningococcal group B vaccine) per the Schedule of Assessments if determined to be eligible for the study at the end of the run-in period.
- If required locally, patients will receive prophylactic antibiotics according to the local standard of care after randomization to cemdisiran or placebo.

#### 5.3.2.2. Pneumococcal and Hib Vaccinations

Patients will receive vaccinations for Hib and *Streptococcus pneumoniae*, if not previously vaccinated, according to current national/local vaccination guidelines for vaccination use. Hib and pneumococcal vaccinations (if required at Screening per national/local guidelines;

vaccination should occur prior to Week-2. At Screening, patient vaccination records will be checked for compliance with local recommendations for the use of these vaccines.

## 5.4. Treatment Compliance

Compliance with study drug administration will be verified through observation by study staff or trained home healthcare professionals.

## 5.5. Other Requirements

### 5.5.1. Contraception

Females of child-bearing potential must be willing to use a highly effective method of contraception from 14 days before first dose, throughout study participation, and for 90 days after last dose administration or until study completion.

Birth control methods which are considered highly effective include:

- Placement of an intrauterine device.
- Placement of an intrauterine hormone-releasing system.
- Bilateral tubal occlusion.
- Surgical sterilization of male partner (with the appropriate post-vasectomy documentation of the absence of sperm in the ejaculate; for female patients on the study, the vasectomized male partner should be the sole partner for that patient).
- Established use of oral (except low-dose gestagens), implantable, injectable, or transdermal hormonal methods of contraception. Females of child-bearing potential who use hormonal contraceptives as a method of contraception must also use a barrier method (condom or occlusive cap [diaphragm or cervical/vault cap] in conjunction with spermicide [eg, foam, gel, film, cream, or suppository]).
- True sexual abstinence, when in line with the preferred and usual lifestyle of the patient. Periodic abstinence (eg, calendar, ovulation, symptothermal, post-ovulation methods) and withdrawal are not acceptable methods of contraception. Abstinent patients must agree to use one of the above-mentioned contraceptive methods if they start sexual relationships during the study and for up to 90 days after the last dose of study drug.

Investigators should advise females of childbearing potential of the most appropriate birth control method available within their country taking into account local medical practice.

Females of child-bearing potential include female patients who have experienced menarche (or begin menarche over the course of the study) and who are not postmenopausal or permanently sterilized (eg, bilateral tubal occlusion, hysterectomy, or bilateral salpingectomy). A postmenopausal state is defined as the absence of menses for 12 months without an alternative medical cause, confirmed by follicle stimulating hormone level within the postmenopausal range.

For male patients, no contraception is required. However, use by males of contraception (condom) may be required in some countries e.g. France, in order to comply with local requirements as described in the corresponding patient consent forms

Compliance with contraception requirements will be assessed on a regular basis by the Investigator throughout the course of the study (see Section [6.7.5.2](#)).

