During the run-in period, patients will visit the study center 14, 8, and 2 weeks prior to randomization (Weeks 0, 6 and 12 of the run-in period). Patients will then return to the study center every 4 weeks after the start of study drug treatment period. The primary endpoint will be assessed at the end of treatment at Week 32.

At the end of treatment (Week 32), patients in the two treatment arms will enter the optional OLE period where they will receive cemdisiran at a dose of 600 mg every 4 weeks in combination with standard of care for 52 weeks. The first study drug administration of the OLE will be administered at Week 36. Patients will return to the study center at Week 40 and every 8 weeks thereafter during the OLE. Home visits, where locally feasible, may be arranged for cemdisiran administration in between 8-weekly study center visits (Weeks 44, 52, 60, 68 and 76), unless patients are required to visit the study center as judged necessary by the Investigator, or if home visits cannot be arranged. An end of treatment (EOT) visit will occur at Week 80 (OLE EOT) and an end of study (EOS) or early termination (ET) visit will be completed at Week 84 (OLE EOS/ET). For patients who complete the treatment period only who do not consent to continue to participate in the study in the OLE period, the EOS/ET visit will be at Week 36.

Patients will return to the clinical study center for safety follow-up visits approximately 13, 26, 39 and 52 weeks after the EOS/ET visit (regardless if EOS/ET visit is at Week 36 or Week 84), unless enrolled in another study with cemdisiran. Home visits, where locally feasible, may be arranged during safety follow-up at 13 and 39 weeks after the EOS/ET visit (regardless if EOS/ET visit is at Week 36 or Week 84).

Regular reviews of safety and tolerability data will be performed by an independent data monitoring committee (DMC) throughout the study with the primary purpose of protecting the safety of participating patients and the integrity of the study.

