### **3.3. Duration of Study**

The maximum estimated total time on study, inclusive of Screening (maximum of 90 days), run-in period (14 weeks), treatment period (36 weeks), optional OLE period (52 weeks) and safety follow-up (52 weeks), is approximately 36 months or 3.0 years.

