#### **3.3.1. Definition of End of Study for an Individual Patient**

A patient is considered to have reached the end of the study if the patient has completed the EOS visit (Week 36 for those patients who do not consent to continue to participate in the study in the OLE period and Week 84 for patients who enter the OLE period). Upon study completion (regardless if EOS visit is at Week 36 or Week 84) patients will enter a safety follow-up period with visits scheduled at intervals of 13 weeks.

For patients withdrawing from the study after receiving one dose of cemdisiran at a minimum (ET), all efforts should be made to conduct the EOS/ET assessments. Patients should then be encouraged to enter the safety follow up period.

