#### Patient and Disease Characteristics

2. Clinical diagnosis of primary IgAN as demonstrated by historical biopsy collected within 60 months of Screening
3. Treated for IgAN with stable, optimal pharmacological therapy. In general, stable and optimal treatment will include maximum allowed or tolerated ACE inhibitor or an ARB for at least 3 months prior to start of run-in period
4. Urine protein  $\geq 1$  g/24-hour at Screening and mean urine protein  $\geq 1$  g/24-hour from two valid 24-hour urine collections at the end of the run-in period, prior to randomization
5. Hematuria as defined by  $\geq 10$  RBCs per high powered field (RBC/hpf) at Screening
6. Females of child-bearing potential must have a negative pregnancy test, cannot be breast feeding, and must be willing to use a highly effective method of contraception 14 days before first dose, throughout study participation, and for 90 days after last dose administration
7. Previously vaccinated with meningococcal group ACWY conjugate vaccine and meningococcal group B vaccine or willingness to receive these vaccinations as well as prophylactic antibiotic treatment, if required by local standard of care
8. Previously vaccinated or willingness to receive vaccinations for Hib and *Streptococcus pneumoniae* according to current national/local vaccination guidelines for vaccination use

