#### **6.7.4.      Electrocardiogram**

Twelve-lead ECGs reporting rhythm, ventricular rate, RR interval, PR interval, QRS duration, and QT interval and Fridericia-corrected QT interval will be obtained, as specified in the Schedule of Assessments ([Table 1](#) and [Table 2](#)). Patients should be supine for at least 5 minutes before each ECG is obtained. A single 12-lead ECG will be performed at Screening. At all other time points, 12-lead ECGs will be performed in triplicate, with readings approximately 1 minute apart. 12-lead ECGs will be performed at predose; 60 minutes postdose; and 4 hours postdose in relation to the Day 1 and Week 32 cemdisiran or placebo doses.

When ECG and blood sample collection occur at the same time, ECGs should be performed before blood samples are drawn.

The Investigator or qualified designee will review all ECGs to assess whether the results have changed since the Baseline visit and to determine the clinical significance of the results. These assessments will be recorded on the eCRF. Additional ECGs may be collected at the discretion of the Investigator, or as per DMC advice.

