#### **6.7.6.7. Pregnancy Reporting**

If a female patient becomes pregnant during the study through 90 days following the last dose of study drug, the Investigator must report the pregnancy to the Sponsor or designee within 24 hours of being notified of the pregnancy. Details of the pregnancy will be recorded on the pregnancy reporting form. The patient should receive any necessary counseling regarding the risks of continuing the pregnancy and the possible effects on the fetus.

The pregnancy should be followed by the Investigator until completion. At the completion of the pregnancy, the Investigator will document the outcome of the pregnancy. If the outcome of the pregnancy results in a postpartum complication, spontaneous abortion, stillbirth, neonatal death, or congenital anomaly, then the Investigator should follow the procedures for reporting an SAE as outlined in Section 6.7.6.4.

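### The contraception rule in Section 5.5.1 can be read to end at Week 36, 28 days after the last dose, although the protocol elsewhere uses 90 days

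*Protocol*

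**What the plan says.** The opening sentence of Section 5.5.1 sets the contraception period to run "throughout study participation, and for 90 days after last dose administration or until study completion". It gives no rule for choosing between the last two limits.

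Three other current statements use 90 days after the last dose and offer no alternative:

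- Inclusion criterion 6 (Section 4.1): "throughout study participation, and for 90 days after last dose administration".
- The abstinence bullet in Section 5.5.1, which binds abstinent women to a listed method "if they start sexual relationships during the study and for up to 90 days after the last dose of study drug".
- Section 6.7.6.7, on the pregnancies that must be reported: "If a female patient becomes pregnant during the study through 90 days following the last dose of study drug". This is a reporting window and not a contraception rule, but it shows the period the sponsor regards as relevant.

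Section 3.3.1 shows how the protocol uses the term: "Upon study completion (regardless if EOS visit is at Week 36 or Week 84) patients will enter a safety follow-up period". Completion there is the end-of-study visit, and follow-up comes after it.

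**The concern.** If *study completion* in Section 5.5.1 has the meaning it has in Section 3.3.1, the alternative limit falls before the 90 days have passed. A site could then tell a woman who does not enter the extension that she may stop contraception at Week 36. That is shorter than the period in which the protocol still requires a pregnancy to be reported. It also treats women within one section differently: an abstinent woman who becomes sexually active is held to 90 days, while a woman already using contraception is offered an alternative.

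This is an operative safety rule. Nothing in the sample size, the primary analysis or any endpoint depends on it.

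**Working it through.** **Inputs**

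- Last dose of the randomized period: Week 32. Section 6.7.4 confirms that a dose is given then, since it times ECGs at "4 hours postdose in relation to the Day 1 and Week 32 cemdisiran or placebo doses".
- End-of-study visit without the extension: Week 36 (Sections 3.1 and 3.3.1).
- First visit after that: Section 3.1 plans "safety follow-up visits approximately 13, 26, 39 and 52 weeks after the EOS/ET visit".
- Day numbers come from the legible schedule of assessments, which is the Amendment 1 table: Week 32 = Day 224 ± 3, Week 36 = Day 252 ± 3, first follow-up visit (Week 49) = Day 343 ± 14.

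**Woman who declines the extension**

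- Short reading: 252 − 224 = 28 days after the last dose.
- Shortfall against 90 days: 90 − 28 = 62 days.
- The 90-day mark is 224 + 90 = Day 314, about Week 45 (314 / 7 = 44.9).
- First follow-up visit: 252 + 13 × 7 = Day 343, which is 343 − 224 = 119 days after the last dose.
- Even with the earliest follow-up date and the latest dosing date, the interval is (343 − 14) − (224 + 3) = 102 days.

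So no scheduled visit falls after Week 36 and before the 90-day mark.

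**Woman who completes the extension (end-of-study visit at Week 84)**

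- Last dose at Week 76: (84 − 76) × 7 = 56 days, which is 90 − 56 = 34 days short.
- If a dose is also given at Week 80: (84 − 80) × 7 = 28 days, which is 62 days short. The legible text does not establish a Week 80 dose, so this is shown only as the other end of the range.

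**The two readings side by side**

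| Meaning of study completion | Contraception after a Week 32 last dose |
|---|---|
| End-of-study visit, as in Section 3.3.1, with the shorter limit governing | 28 days |
| End of the 52-week safety follow-up, or the later limit governing | at least 90 days |

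The text does not choose between these rows.

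**The case against.** The best case for leaving the wording alone is that the short reading fits poorly with the rest of the protocol.

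- Section 3.3 counts follow-up as time on study: "optional OLE period (52 weeks) and safety follow-up (52 weeks), is approximately 36 months or 3.0 years". Section 4.3.2.1 likewise treats entry into safety follow-up as remaining in the study. If participation includes those 52 weeks, the first limb of the sentence already covers the 90 days and the added clause does no harm.
- The sentence is conjunctive. Participation already lasts at least until the end-of-study visit, so a completion date of Week 36 would add nothing to it.
- The Amendment 1 summary of changes gives European contraception guidance as the purpose of the edit that brought in the clause, and the same edit tightened the permitted methods. An intended cut from 90 to 28 days is unlikely.
- Section 5.5.1 also requires regular compliance checks by the investigator, and pregnancies up to 90 days remain reportable.

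The first three points stand as evidence of intent. They show that the clause is ambiguous and that the sponsor probably did not mean 28 days. They do not remove the conflict: Section 3.3.1 is the section that defines the end of study for an individual patient, it uses the same term, and it places follow-up after it. On the long reading, moreover, the 90-day figure is redundant for anyone who completes follow-up.

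The compliance checks do not close the gap, because no visit is scheduled inside it. Pregnancy reporting captures an event after it has happened. Inclusion criterion 6 tests willingness at entry, so it is not itself breached by stopping early.

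**Conclusion.** The concern holds as an ambiguity in a safety rule. Read with the protocol's own use of the term, Section 5.5.1 permits contraception to stop 28 days after the last dose, 62 days short of the 90 days used in the three other places. For women completing the extension the shortfall is 34 days after a Week 76 last dose, or 62 days if a Week 80 dose is given. The documents do not show that early stopping would in fact occur: that depends on consent wording and site counselling, which were not available. Since no visit falls in the gap, what a woman is told at Week 36 carries most of the weight.

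The reach is small. It covers women of child-bearing potential among about 30 randomized patients, and mainly those who decline the extension. There is no effect on the analysis.

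The conclusion rests on the Amendment 2 text of Section 5.5.1, the most recent version in the material reviewed, and on visit days from the Amendment 1 schedule. The week numbers in the current Sections 3.1, 3.3.1 and 6.7.4 give the same nominal intervals.

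**What to change.** In the first sentence of Section 5.5.1, delete the four words that follow the 90-day limit. The sentence then agrees with inclusion criterion 6, the abstinence bullet and Section 6.7.6.7. Alternatively, keep the clause and state that the later of the two dates applies. Either way the minimum becomes 90 days after the last dose, which for a Week 32 last dose is Day 314. If the consent form carries the same clause, change it there too.

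The cost is one clause in the protocol and possibly one in the consent form. No visit, test or analysis is added or altered.
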